2 PROTOCOL SYNOPSIS

T			
Title	An Efficacy and Safety Study of Ivacaftor in Patients With Cystic Fibrosis		
	and Splicing Mutations		
Clinical Phase	N of 2 Study		
Objective	To evaluate the efficacy and safety of ivacaftor in two patients (sisters)		
	who have a splicing mutation and pancreatic sufficiency		
Endpoints	Primary		
	Absolute change in percent predicted forced expiratory volume in		
	1 second (FEV ₁) from baseline through Week 24		
	Key Secondary		
	Relative change in percent predicted FEV1 from baseline through		
	Week 24		
	Achievement of mycobacterial culture conversion (negative		
	culture) by Week 24		
	 Secondary Safety and tolerability assessments based on adverse events (AEs), 		
	clinical laboratory values (i.e., liver function tests)		
	Absolute change in sweat chloride from baseline through Week 24		
	Absolute change in respiratory symptom scores from baseline at		
	Week 24		
Study	Sisters with specific mutations		
Population			
Number of	2		
Subjects			
Study	Subjects will be treated for 6 months and followed for 7 months		
Duration			
Study Design	This postmarketing N of 2 study is designed to evaluate the efficacy and		
	safety of open-label ivacaftor treatment in two sisters with cystic fibrosis		
	and pancreatic sufficiency. They have a splicing mutation that is predicted		
	to respond favorably to ivacaftor therapy. In addition to measurement of		
	usual clinical outcomes (i.e. lung function, nutritional status), there is great		
	interest on the impact on nontuberculous mycobacteria (NTM) airways		
	infection.		
	Subjects will undergo sputum cultures at baseline and monthly during		
	treatment, initially in the absence of anti-NTM therapy but with the intent		
	to treat with antibiotics if there is persistence of the infection in cultures.		
	Other clinical outcomes will include changes in sweat chloride, lung		
	function and weight. Safety measures will include periodic assessment of		
Assessments	liver enzymes. All serious and non-serious adverse events will be collected		
Assessifients	Efficacy: spirometry, sweat chloride testing, CRISS, sputum cultures		
	(bacteria and mycobacteria), height, and weight Safety: AEs, clinical laboratory assessments (liver function tests), vital		
	signs, physical examinations, and pulse oximetry		
Statistical	Statistical analysis details will be provided in the Statistical Analysis Plan		
Analyses	(SAP), which will be finalized before the clinical data lock for the study.		
Allalyses	(5.11), which will be illianzed before the chinear data lock for the study.		

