3 SCHEDULE OF ASSESSMENTS

The Schedule of Assessments is shown in Table 3-1

	Visit 1	Visit 2	Visit 3	Visit 4	Visit 5	Visit 6	Visit 7	Visit 8
Event/Assessment	Day 1	Day 30	Day 60	Day 90	Day 120	Day 150	Day 180	Day 210
Informed consent	X							
Medical history	х							
Demographics ^a	х							
Physical examination	Х	×	×	х	x	×	×	х
Height and weight	х	х	х	х	х	х	х	х
Sweat test	х	х		х			х	х
Spirometry	х	х	х	х	х	х	х	х
Genetic testing ^b	х							
Liver function tests ^c	х			х			х	
Sputum cultures ^d	х	х	х	х	х	х	х	х
CRISS	Х	Х	Х	х	х	Х	Х	х
Adverse events		Х	Х	х	х	Х	х	х
Concomitant medications	х	х	х	х	х	х	х	х
Study drug dispensed	х	х	х	х	х	х		

Demographics include sex, race, and age. Baseline characteristics include age at CF diagnosis, CFTR genotype Genetic testing will get confirm that the two mutations are not on the same allele (with a cryptic additional mild mutation on the other allele)._

Safety labs include liver enzymes (ALT, AST, GGT)_
Sputum will be tested for bacteria and mycobacteria (including AFB smear and culture). Susceptibility testing will not be performed

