9 STUDY DESIGN

9.1 Overview of Study Design

This postmarketing N of 2 study is designed to evaluate the efficacy and safety of open-label ivacaftor treatment in two sisters with cystic fibrosis and pancreatic sufficiency. They have a splicing mutation that is predicted to respond favorably to ivacaftor therapy. In addition to measurement of usual clinical outcomes (i.e. lung function, nutritional status), there is great interest on the impact on nontuberculous mycobacteria (NTM) airways infection.

Subjects will undergo sputum cultures at baseline and monthly during treatment, initially in the absence of anti-NTM therapy but with the intent to treat with antibiotics if there is persistence of the infection in cultures. Other clinical outcomes will include changes in sweat chloride, lung function, respiratory symptoms (CRISS), and weight. Safety measures will include periodic assessment of liver enzymes. All serious and non-serious adverse events will be collected

9.1.1 Day 1

The investigator will obtain informed consent from the subjects (Note: they have already expressed interest in participation prior to protocol development but are aware of planned study procedures). Subjects will have blood drawn for genetic testing and undergo a physical examination, including height and weight, and measurement of baseline measures for efficacy and safety (i.e. sweat test, spirometry, respiratory symptoms (CRISS), sputum cultures for bacteria and mycobacteria, and liver enzyme testing). The subjects will commence dosing of ivacaftor on this day.

9.1.2 Months 1, 2, 3, 4, 5, and 6

Patients will be evaluated for any changes in health or medications. They will undergo physical examination, including height and weight. They will undergo measurement of efficacy outcomes (sweat test, spirometry, CRISS, sputum cultures) and safety (liver enzyme tests) as per the Study Assessment Schedule (Table 3-1).

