9.2 Rationale for Study Design

The primary efficacy measures (changes in sweat chloride, respiratory symptoms, and spirometry) are expected to change in the short term (i.e. 2-4 weeks) as shown in clinical trials, but measurement through the duration of the study will demonstrate persistence of effect with chronic therapy. The other key assessment will be the change in sputum culture results, especially related to mycobacteria. It is expected that these changes will take more time to be realized, accounting for the planned 6 months of therapy and monitoring.

As this is an n-of-2 study, there is no value to a blinded aspect for the study. Treatment will be open-label and clinical outcomes will be assessed by the individuals.

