11.4 Prior and Concomitant Medications

Information regarding all medications administered before study enrollment and through the last study visit will be recorded.

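### As worded, the key secondary NTM conversion endpoint can count a negative culture taken after the planned anti-NTM antibiotics, so persistence on ivacaftor can be scored as conversion

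*Combined protocol and SAP*

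**What the plan says.** The synopsis lists as a key secondary endpoint "Achievement of mycobacterial culture conversion (negative" culture, in the singular, with Week 24 as the outer limit. That is the only definition of conversion in the text available. Section 8 names sputum microbiology as a secondary measure, with semi-quantitative smear and culture results, and does not define conversion. Section 12.3.3 gives formulas for absolute and relative change only, with no rule for a yes/no outcome. Section 12.3 defers detail to an SAP to be finalised before database lock.

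The synopsis and Section 9.1 describe monthly cultures taken "initially in the absence of anti-NTM therapy but with the intent to treat with antibiotics if there is persistence of the infection in cultures". Neither states what counts as persistence or when antibiotics would begin.

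On timing, the synopsis says "Subjects will be treated for 6 months and followed for 7 months". Table 3-1 schedules sputum cultures on Days 1, 30, 60, 90, 120, 150, 180 and 210.

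On recording antibiotics, the sections disagree. Section 11.4 says "Information regarding all medications administered before study enrollment and through the last study visit will be recorded". Table 3-1 has a row for "Concomitant medications" marked at all eight visits, and Section 9.1.2 says "Patients will be evaluated for any changes in health or medications". Section 12.3.2.3 opens by restricting collection to corticosteroids and ivacaftor.

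**The concern.** The study's objective is the efficacy and safety of ivacaftor, and the design section singles out its effect on NTM infection. Antibiotics are intended for exactly the sister in whom ivacaftor alone has not cleared the organism. If her culture turns negative after antibiotics start and before Week 24, the endpoint as worded records a conversion. The wording also accepts one unconfirmed negative, even if a later culture is positive.

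With two subjects, one such classification is half of the result on this endpoint. Separating ivacaftor from antibiotics afterwards requires antibiotic dates, and one section, if followed, would leave them uncollected.

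**Working it through.** The plan gives no conversion rate, power or error rate to reproduce. The check is a count from Table 3-1, a comparison of sections, and one illustration under stated assumptions.

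**Step 1: the window.** Week 24 is 24 × 7 = Day 168. On-treatment cultures by then are Days 30, 60, 90, 120 and 150: five. No visit falls on Day 168. Day 180 is 180 / 7 = 25.7 weeks. It is a reasonable reading of Week 24, because treatment is planned for six months and Visit 7 is the Day 180 visit; on that reading there are six cultures. Both are carried forward.

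**Step 2: cultures exposed to antibiotics.** If antibiotics start after the k-th on-treatment culture, n − k cultures in the window follow the start.

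| Antibiotics start after the culture on | k | Exposed, n = 5 (to Day 168) | Exposed, n = 6 (to Day 180) |
|---|---|---|---|
| Day 30 | 1 | 4 | 5 |
| Day 60 | 2 | 3 | 4 |
| Day 90 | 3 | 2 | 3 |
| Day 120 | 4 | 1 | 2 |
| Day 150 | 5 | 0 | 1 |

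Any one negative among the exposed cultures satisfies the endpoint as worded. The probability of such a negative is not in the documents, and no value is assumed here.

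**Step 3: single unconfirmed negatives (illustration only).** Let s be the chance that a culture is positive when infection is present. The documents give no value; 0.95 to 0.70 is assumed. Assume also that the infection never clears and that cultures are independent. Then:

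- at least one negative among n cultures: 1 − s^n;
- two consecutive negatives with no later positive, no antibiotics in the window: the last two cultures must both be negative, so (1 − s)².

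| s | 1 − s^5 | 1 − s^6 | (1 − s)² |
|---|---|---|---|
| 0.95 | 23% | 26% | 0.25% |
| 0.90 | 41% | 47% | 1% |
| 0.80 | 67% | 74% | 4% |
| 0.70 | 83% | 88% | 9% |

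For example, 1 − 0.90^5 = 1 − 0.590 = 0.410. These figures show why a confirmation rule matters. They do not measure the antibiotic problem in Step 2, and correlated false negatives would change them.

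**Step 4: can antibiotics be identified?** Section 11.4, Table 3-1 and Section 9.1.2 support capturing them; Section 12.3.2.3 does not. Section 13.1.3 asks for treatment given for adverse events, but Section 13.1.1 defines those as new or worsened conditions. Antibiotics for an unchanged, pre-existing infection need not appear there.

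**The case against.** The strongest reply is that this is an uncontrolled, descriptive study of two people with no hypothesis test. Section 12.3.1 promises listings of all subject data, so a reader could see an isolated negative or a later positive. Since antibiotics are intended only on persistence, a recorded start would itself signal that ivacaftor alone had not cleared the infection. The pending SAP may also define conversion. Much of this stands, and it limits the effect. It does not remove the point: listings do not correct the classification, they reveal antibiotic timing only if it is recorded, and an SAP finalised just before lock in an open-label study analysed by the investigator could be written with culture results known.

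Four stronger readings are tempting but unsupported:

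- *That a false conversion is likely.* No antibiotic start time or clearance rate is given. Section 9.2 says of culture results, "It is expected that these changes will take more time to be realized", and antibiotics might start too late to affect any culture in the window.
- *That antibiotic dates will be missing.* Most of the text says they will be captured, and Section 12.3.2.3 itself refers to Section 11.4 for the collection period. This is a contradiction to reconcile, not an established loss of data.
- *That the Step 3 percentages are the trial's error rates.* They follow from assumed sensitivity and independence.
- *That two consecutive negatives is the required standard.* The documents set no number.

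**Conclusion.** The point holds as a defect of definition. The endpoint as worded does not separate conversion on ivacaftor from conversion on ivacaftor plus antibiotics, although the design anticipates the second. Between 0 and 4 of five cultures, or 1 and 5 of six, would be exposed, depending on when antibiotics start and which visit is Week 24. This range rests only on Table 3-1 and on a start after one of the Day 30 to Day 150 cultures. The chance of misclassification cannot be derived from the documents. Two gaps add to it: no confirmation rule is stated, and no positive baseline culture is required, although conversion presupposes one and the inclusion criteria in Section 10.1 do not ask for it. The finding applies to the text available, which includes no separate SAP. Attribution to ivacaftor would remain limited in an uncontrolled study even with the wording repaired.

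**What to change.** 1. Score conversion on ivacaftor only in a sister with a positive baseline culture, and only from cultures taken before any anti-NTM antibiotic. Report a sister who starts antibiotics before meeting the definition as *not converted on ivacaftor alone*, and list her later cultures separately as ivacaftor plus antibiotics.
2. Reconcile Section 12.3.2.3 with Section 11.4 and Table 3-1 so that antibiotic start and stop dates are captured.
3. Before any on-treatment culture result is seen, fix in writing a confirmation rule, which visit is Week 24, and whether the Day 210 culture, taken after the planned six months of treatment, may confirm a Day 180 negative. One possible rule is two consecutive negatives with no later positive in the antibiotic-free period; the number is the sponsor's choice.

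No change to when antibiotics are given is proposed.

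The cost is wording in the endpoint and SAP, one reconciled statement, and a CRF change if the form follows Section 12.3.2.3. No visit or sample is added. The drawback is that late conversions may be left unconfirmed. Under a two-negative rule, the first negative must come by Day 120 if the window closes at Day 168, or by Day 150 if it closes at Day 180, unless a later culture is allowed to confirm. An early antibiotic start shortens the evaluable period further.

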3 SCHEDULE OF ASSESSMENTS

The Schedule of Assessments is shown in Table 3-1

	Visit 1	Visit 2	Visit 3	Visit 4	Visit 5	Visit 6	Visit 7	Visit 8
Event/Assessment	Day 1	Day 30	Day 60	Day 90	Day 120	Day 150	Day 180	Day 210
Informed consent	X							
Medical history	х							
Demographics ^a	х							
Physical examination	Х	×	×	х	x	×	×	х
Height and weight	х	х	х	х	х	х	х	х
Sweat test	х	х		х			х	х
Spirometry	х	х	х	х	х	х	х	х
Genetic testing ^b	х							
Liver function tests ^c	х			х			х	
Sputum cultures ^d	х	х	х	х	х	х	х	х
CRISS	Х	Х	Х	х	х	Х	Х	х
Adverse events		Х	Х	х	х	Х	х	х
Concomitant medications	х	х	х	х	х	х	х	х
Study drug dispensed	х	х	х	х	х	х		

Demographics include sex, race, and age. Baseline characteristics include age at CF diagnosis, CFTR genotype Genetic testing will get confirm that the two mutations are not on the same allele (with a cryptic additional mild mutation on the other allele)._

Safety labs include liver enzymes (ALT, AST, GGT)_
Sputum will be tested for bacteria and mycobacteria (including AFB smear and culture). Susceptibility testing will not be performed

5 LIST OF ABBREVIATIONS

Abbreviation	Definition
ALT	Alanine transaminase
AST	Aspartate transaminase
BMI	body mass index
CF	cystic fibrosis
CFF	Cystic Fibrosis Foundation
CFTR	CF transmembrane conductance regulator gene
CFTR	CF transmembrane conductance regulator protein
CRF	case report form
EDC	electronic data capture
EU	European Union
FEV_1	Forced expiratory volume in one second
G551D	CFTR missense gene mutation that results in the replacement of a glycine residue at position 551 of CFTR with an aspartic acid residue
G551D	CFTR protein with a replacement of a glycine residue at position 551 with an aspartic acid residue
GCP	Good Clinical Practice
GGT	Gamma-glutamyl transaminase
HIPAA	Health Insurance Portability and Accountability Act
ICF	informed consent form
IEC	independent ethics committee
IRB	institutional review board
MAC	Mycobacteria avium complex
MedDRA	Medical Dictionary for Regulatory Activities
NTM	Non-tuberculous mycobacteria
SAE	serious adverse event
SAP	statistical analysis plan
SD	standard deviation
US	United States
WHO-DD	World Health Organization Drug Dictionary

6 INTRODUCTION

Overview of Cystic Fibrosis

Cystic fibrosis (CF) is a chronically debilitating autosomal recessive disease with high morbidity and premature mortality that affects approximately 30,000 individuals in the United States (US)¹ and 36,000 individuals in the European Union (EU).² The disease is caused by mutations in the CF transmembrane conductance regulator gene (CFTR), which results in absent or deficient function of the CF transmembrane conductance regulator protein (CFTR) at the cell surface. 4 CFTR is an epithelial chloride channel responsible for helping to regulate salt and water absorption and secretion in various tissues. The failure to regulate chloride transport in these organs results in the multisystem pathology associated with CF.⁵ In the lungs, obstruction of airways with thick mucus, establishment of a chronic bacterial infection in the airways, and damaging inflammatory responses are all thought to play a role in causing irreversible structural changes in the lungs and, ultimately, respiratory failure. Progressive loss of lung function is the leading cause of mortality. 1,3 Currently there is no cure for CF, and, despite adjunctive treatments with nutritional supplements, antibiotics, and mucolytics⁶, the median predicted age of survival of individuals born today with CF is approximately 40 years of age.^{1,7}

More than 1800 mutations in the *CFTR* gene have been identified. Mutations in the *CFTR* gene have been classified based on the molecular and functional consequence of the mutation on the CFTR protein 9,10,11 and can be generally considered to reduce the quantity of functional CFTR protein that reaches the epithelial cell surface or reduce the function of CFTR protein located at the cell surface. *CFTR* gene mutations that affect the quantity of functional cell surface CFTR protein include defects that reduce CFTR protein synthesis and defects that impede the cellular processing and delivery of CFTR proteins to the cell surface.

CFTR gene mutations associated with minimal CFTR function include

- mutations associated with severe defects in the ability of the CFTR channel to open and close, known as defective channel gating or "gating mutations";
- defects in the cellular processing and delivery to the cell surface;
- no (or minimal) CFTR synthesis; and
- · severe defects in channel conductance.

One approach to increasing the level of chloride transport through the CFTR channels is to treat with a potentiator, a compound that increases the channel gating activity of CFTR protein located at the cell surface, resulting in increased chloride transport. ^{10,12} Potentiators represent a therapeutic strategy to treat CF. A modest restoration of chloride secretion through the action of a potentiator could prevent the hyperabsorption of water across the apical surface of epithelial cells, allowing for proper maintenance of airway hydration. Adequate airway hydration could alleviate the cycle of mucus plugging, infection, and inflammation that leads to irreversible structural changes in the lungs, and eventually respiratory failure for patients with CF. There is a supposition that potentiators can facilitate chloride secretion in patients with CF who express at least some amount of residual CFTR protein at the cell surface. ¹³

Overview of Ivacaftor and Rationale for Study

Ivacaftor, a compound developed by Vertex Pharmaceuticals Incorporated, is classified as a CFTR potentiator. Commercially-available ivacaftor (KalydecoTM, 150-mg tablets) was approved in the US and the EU in 2012 for the treatment of CF in patients 6 years of age and older who have the *G551D* mutation in the *CFTR* gene. The indication for ivacaftor has since been expanded to include additional mutations (*G1244E*, *G1349D*, *G178R*, *G551S*, *S1251N*, *S1255P*, *S549N*, *S549R*, and *R117H*) based on the demonstration of clinical efficacy. Ivacaftor is an orally bioavailable small molecule CFTR potentiator that targets the underlying defect in CF. As such, ivacaftor is a member of a new class of drugs, known in the literature as CFTR modulators, that provides a new therapeutic approach to the treatment of CF.

7 STUDY OBJECTIVE

To evaluate the efficacy and safety of ivacaftor in two sisters known to have a splicing mutation of CFTR.

8 STUDY ENDPOINTS

- The primary measures of efficacy will include spirometry and sweat chloride compared to baseline.
- Secondary measures of efficacy will include change in weight (BMI), respiratory symptoms (CRISS), and sputum microbiology with particular interest in mycobacterial cultures, including semi-quantitative smear and culture results.

9 STUDY DESIGN

9.1 Overview of Study Design

This postmarketing N of 2 study is designed to evaluate the efficacy and safety of open-label ivacaftor treatment in two sisters with cystic fibrosis and pancreatic sufficiency. They have a splicing mutation that is predicted to respond favorably to ivacaftor therapy. In addition to measurement of usual clinical outcomes (i.e. lung function, nutritional status), there is great interest on the impact on nontuberculous mycobacteria (NTM) airways infection.

Subjects will undergo sputum cultures at baseline and monthly during treatment, initially in the absence of anti-NTM therapy but with the intent to treat with antibiotics if there is persistence of the infection in cultures. Other clinical outcomes will include changes in sweat chloride, lung function, respiratory symptoms (CRISS), and weight. Safety measures will include periodic assessment of liver enzymes. All serious and non-serious adverse events will be collected

9.1.1 Day 1

The investigator will obtain informed consent from the subjects (Note: they have already expressed interest in participation prior to protocol development but are aware of planned study procedures). Subjects will have blood drawn for genetic testing and undergo a physical examination, including height and weight, and measurement of baseline measures for efficacy and safety (i.e. sweat test, spirometry, respiratory symptoms (CRISS), sputum cultures for bacteria and mycobacteria, and liver enzyme testing). The subjects will commence dosing of ivacaftor on this day.

9.1.2 Months 1, 2, 3, 4, 5, and 6

Patients will be evaluated for any changes in health or medications. They will undergo physical examination, including height and weight. They will undergo measurement of efficacy outcomes (sweat test, spirometry, CRISS, sputum cultures) and safety (liver enzyme tests) as per the Study Assessment Schedule (Table 3-1).

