12.3.2.3 Prior and Concomitant Medications

Only prior and concomitant corticosteroids and ivacaftor will be collected. Medications taken during the collection period specified in Section 11.4 will be summarized by preferred term using the World Health Organization Drug Dictionary (WHO-DD) for the Safety Set as frequency tables in 2 parts:

- Prior medication: medication that started before the first dose of ivacaftor, regardless
 of when dosing of the medication ended.
- Concomitant medication: medication received at or after the first dose of ivacaftor, medication that was received before initial dosing of ivacaftor and continued after initial dosing, or medication with missing stop date.

Medications that started before the first dose of ivacaftor and continued after the first dose of ivacaftor will be summarized separately as prior medications and concomitant medications, respectively. Medications with a missing start date will be considered to have a start date before the first dose of ivacaftor.

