12.3.3 Efficacy Analysis

Change (absolute change) from baseline will be calculated as post-baseline value - baseline value. Relative change from baseline will be calculated as (post-baseline value - baseline value)/baseline value.

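### The Week 24 culture-conversion endpoint is not restricted to cultures taken before anti-NTM antibiotics, so a conversion on added antibiotics would be reported without distinction in a study of ivacaftor efficacy

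*Combined protocol and SAP*

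**What the plan says.** **Objective.** Section 7: "To evaluate the efficacy and safety of ivacaftor in two sisters known to have a splicing mutation of CFTR".

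**Endpoint.** The first words of the second key secondary endpoint in the synopsis are "Achievement of mycobacterial culture conversion (negative"; the rest of the line requires a negative culture by Week 24. It makes no mention of antibiotics. Section 8 lists sputum microbiology as a secondary measure and includes semi-quantitative smear and culture results.

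**Antibiotics.** Section 9.1, repeated in the synopsis, plans monthly cultures during treatment. Anti-NTM therapy is absent at first, "with the intent to treat with antibiotics if there is persistence of the infection in cultures".

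**Importance and timing.** Section 9.2: "The other key assessment will be the change in sputum culture results, especially related to mycobacteria". It adds: "It is expected that these changes will take more time to be realized, accounting for the planned 6 months of therapy and monitoring".

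**Analysis.** Section 12.3.3 opens with "Change (absolute change) from baseline will be calculated as post-baseline value - baseline value", gives the matching formula for relative change, and ends there. Section 12.3 defers details to an SAP to be finalised before database lock. Section 12 assigns the analysis to the investigator.

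**Medication records.** Section 11.4: "Information regarding all medications administered before study enrollment and through the last study visit will be recorded". Section 12.3.2.3: "Only prior and concomitant corticosteroids and ivacaftor will be collected".

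**The concern.** Under section 9.1, antibiotics are added because the infection has persisted on ivacaftor. A negative culture after that point says something about ivacaftor plus antibiotics and nothing clear about ivacaftor alone. The endpoint wording does not separate the two situations: both give a negative culture by Week 24.

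There is no control arm. For each sister, the order of antibiotic start and first negative culture is therefore the main evidence on whether the infection cleared on ivacaftor alone or on combined therapy. An endpoint that ignores this order could report as a conversion the very case in which ivacaftor alone had not cleared the infection. The plan names culture change as a key assessment and uses it to justify the six-month duration, so the ambiguity touches a main purpose of the study.

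**Working it through.** No figure in the plan can be reproduced here: there is no power calculation, no test and no assumed conversion rate. The check sets the texts side by side.

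**Step 1. Can antibiotics start before the endpoint is assessed?** Week 24 is 24 × 7 = Day 168. Table 3-1 schedules post-baseline cultures on Days 30, 60, 90, 120 and 150, which makes five by Day 168. The Day 180 visit falls at 180 / 7 = 25.7 weeks; if it is taken as the Week 24 visit, there are six. Section 9.1 defines neither persistence nor an earliest start date for antibiotics, and does not defer them until after Week 24. So yes, they can.

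**Step 2. How many cultures could be affected?** The start day is not given, so this only counts visits under assumed start days. If antibiotics begin just after the k-th post-baseline culture, 5 − k of 5 (or 6 − k of 6) later cultures fall on combined therapy:

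| Assumed start just after | Of 5 (by Day 168) | Of 6 (Day 180 counted) |
|---|---|---|
| Day 30 | 4 | 5 |
| Day 60 | 3 | 4 |
| Day 90 | 2 | 3 |
| Day 120 | 1 | 2 |
| Day 150 | 0 | 1 |
| Day 180 | not applicable | 0 |

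The range runs from no overlap to most of the cultures. The early rows would treat a single positive follow-up culture as persistence, which sits poorly with the slow change that section 9.2 expects. The table shows that overlap is possible. It does not measure bias.

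**Step 3. How is a negative culture classified?**

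| Course | Endpoint as worded | What it shows |
|---|---|---|
| Positive at baseline, negative by Week 24, no antibiotics | Converted | Clearance on ivacaftor alone, uncontrolled |
| Positive at baseline and on ivacaftor alone, negative by Week 24 after antibiotics | Converted | Clearance on combined therapy |
| Positive throughout | Not converted | No clearance |

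The first two rows receive the same result. Section 12.3.3 does not separate them, and neither does any other section of the text supplied.

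**Step 4. Would the antibiotic dates be on record?** Section 11.4 covers all medications, Table 3-1 marks concomitant medications at all 8 visits, and section 9.1.2 has medication changes reviewed at each monthly visit. Section 12.3.2.3 restricts collection to two items, neither of which is an antibiotic. Followed literally, that sentence would remove the dates that step 3 needs.

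**The case against.** **The plan does not say that post-antibiotic negatives count.** Correct. A reader might infer that the plan deliberately credits them to ivacaftor. The documents do not support that: the endpoint is silent, and the classification follows only from its being unrestricted.

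**Section 12.3 is a summary and the SAP will supply the rule.** It may. Section 12.3 introduces itself as a summary of the safety analyses, so the brevity of 12.3.3 is weak evidence on its own. However, the SAP need only be final before database lock, treatment is open-label and the investigator analyses the data, so a rule could be written after the cultures are known. That is a possibility shared by every deferred rule in this study, and nothing suggests that it is intended.

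**With two subjects, the listings are enough.** Largely fair. Section 12.3.1 lists all subject data and section 8 includes semi-quantitative results. A reader could rebuild each sister's sequence if the antibiotic dates are recorded. The reported endpoint would still read the same in both cases.

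**The medication conflict is editorial.** Probably. The next sentence of 12.3.2.3 itself refers back to the collection period in 11.4. A reader might infer that the antibiotic dates will be lost. Three other places point to capture, so the documents support only a contradiction to be removed.

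**Conversion regardless of added antibiotics is a legitimate outcome.** Yes, if it is labelled as such. It does not by itself answer a question about ivacaftor alone.

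**Conclusion.** The point holds as a gap in the endpoint definition. The endpoint is unrestricted, antibiotics are intended during ivacaftor treatment if infection persists, and no supplied text separates negatives obtained before antibiotics from those obtained after. The conflict between 12.3.2.3 and 11.4 adds to it, because it concerns the dates needed to make the separation.

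The consequence is limited to attribution of a descriptive secondary outcome in two subjects. There is no hypothesis test, so no error rate is affected, and the FEV1 endpoint is outside this point. No numeric magnitude can be derived: the documents give no antibiotic start day and no conversion rate with or without antibiotics, so a reader should not infer a particular degree of inflation.

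The conclusion assumes that at least one sister is culture-positive at baseline. Section 9.1 implies this by speaking of persistence, but the inclusion criteria do not require it. It also assumes that antibiotics may start before the last culture counted for Week 24, which the text permits but does not schedule.

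**What to change.** 1. **Synopsis endpoint and section 12.3.3.** For each sister culture-positive at baseline, report separately (a) conversion by Week 24 on cultures collected before the start of any anti-NTM antibiotic and (b) conversion by Week 24 on cultures collected after that start. Classify cultures by collection date.
2. **Interpretation.** Describe only (a) as occurring on ivacaftor alone, and state that the uncontrolled design does not prove causation even then.
3. **Section 12.3.2.3.** Align it with 11.4 so that the name, start date and stop date of each anti-NTM antibiotic are recorded.
4. **Clinical care.** Leave antibiotic timing to clinical judgement.

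The rule should be in place before post-baseline cultures are known.

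**Cost.** Edits to three places in the text and, if not already present, CRF fields for antibiotic name and dates. No visits or cultures are added. The downside is that fewer conversions may be credited to ivacaftor than under the current wording, and the period observed on ivacaftor alone may prove shorter than six months.
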